**12.1.3. Hypotheses**

**H0:** The five (5) year chronic lead-related complication-free rate  $\leq 92.5\%$

**HA:** The five (5) year chronic lead-related complication-free rate  $> 92.5\%$

The null hypothesis (H0) will be rejected if the lower one-sided 95% confidence bound for the chronic lead-related complication-free rate is greater than 92.5% (*i.e.*, HA, the alternative hypothesis).

**12.1.4. Study Subject Sample Size**

[Redacted]

[Redacted]

[Redacted]

[Redacted]	[Redacted]	[Redacted]	[Redacted]	[Redacted]	[Redacted]
[Redacted]	[Redacted]	[Redacted]	[Redacted]	[Redacted]	[Redacted]

[Redacted]

## **12.2. Number of Subjects per Investigative Site**

In order to ensure geographical dispersion of investigational sites, individual study sites may not enroll more than twenty percent (20%) of the anticipated enrollment ceiling of 1,780 subjects (*i.e.*, not more than 356 subjects at any single site). It is anticipated that the majority of investigational centers conducting the LSS of 4-SITE Study will enroll about one (1) subject per month.

## **12.3. Data Analyses**

### **12.3.1. Primary Study Endpoint Analysis**

Regarding the 4-SITE Lead and the compatible header in a PG, the primary study endpoint is the evaluation of the proportion of subjects without a chronic 4-SITE Lead/Header-related complication within five (5) years post-implant period. When the final study subject reaches five (5) years of follow-up, the primary analysis will be performed based on the Kaplan-Meier method for the estimation of the five (5) year chronic lead-related complication-free rate, including the lower one-sided 95% confidence interval. The censoring mechanism of the Kaplan-Meier analysis incorporates all available data on study subjects, including those that withdrew or were lost-to-follow-up.

The Kaplan-Meier analysis will begin at the time of implant for each study subject. All subjects who are successfully implanted with the 4-SITE Lead/Header System will be included in the analysis. The endpoint adverse events are defined as complications meeting the criteria described in Sub-section 12.1.2 above. The determination for inclusion of adverse events in the endpoint analysis will be made by an independent Clinical Events Committee (see Sub-section 22.1 hereinafter). Additionally, since this study is focused on chronic 4-SITE Lead/Header System performance, except as noted in Sub-section 12.1.2

above, acute adverse events associated with attempted lead implants will not be included in this analysis. These events fall within the 30 days of an invasive cardiac surgery and do not meet the criteria outlined in Sub-section 12.1.2 above.

### **12.3.2. Additional Analyses/Changes to Planned Analyses**

In addition to the primary endpoint analysis, the adverse events contributing to the endpoint will be analyzed. The individual adverse event rates and 95% upper confidence bounds will be provided.

Any changes to the planned statistical analyses made prior to performing the analyses will be documented in an amended Statistical Analysis Plan approved prior to performing the analyses. Changes from the planned statistical methods after performing the analyses will be documented in the clinical study report along with a reason for the deviation.

### **12.3.3. Subgroup Analyses**

An analysis will be performed for the primary endpoint to determine whether significant differences exist in endpoint results between subgroups. The list of baseline covariates (with applicable subgroups in parentheses) includes, but is not necessarily limited to, the following:

- Sex (Female vs. Male);
- Geography (International vs. United States);
- Age (< 65 years vs. ≥ 65 years); and
- Enrollment Timing (Pre-Implant versus Post-implant).

The baseline covariate will be added to a univariate logistic regression model and a test for significance at the 5% level will be performed. For each baseline covariate in which a significant difference exists between subgroups, the results for each subgroup will be presented separately.

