## 8. Study Design

The LSS of 4-SITE Study is a prospective, non-randomized, multi-center, global clinical investigation of subjects implanted with the 4-SITE Lead/Header System. The LSS of 4-SITE Study is designed to collect product performance information, any reportable adverse events and withdrawal data. Study subjects who are enrolled prior to implantation of the device system will have an enrollment visit during which informed consent is obtained, followed by device system implantation (*i.e.*, day 0) and a pre-discharge visit (0 to 3 days) after implantation, during which a full device system interrogation will be performed. Study subjects who are enrolled after device system implantation (up to 14 days post implant) will undergo an enrollment visit during which informed consent is obtained, followed by information gathered from their implant. Regarding the pre-discharge visit (0 to 3 days post

implant) for subjects enrolled post implant, information from a full device system interrogation is optional and will be provided to Boston Scientific only if it is available.

All study subjects will then have another full device system evaluation performed at the investigational site facility at 30 (+/- 7) days post implant. Thereafter, subjects are required to participate in a follow-up visit (to be performed at the investigational site facility) for a full device system (*i.e.*, pulse generator and lead) evaluation at least once every six (6) months (+/- 30 days). A deviation must be reported if the evaluation is not done within the required follow-up visit window timeframe. Study subjects will be followed for at least five (5) years from the time of implant or until death, withdrawal from the study, or termination/closure of the study. The study design is presented below in Figure 8.1-1.

[figure not shown]
Subjects may be followed on the LATITUDE system (which may include weight scale and blood pressure sensors) from the time they are implanted. However, required LSS of 4-SITE Study follow-ups cannot be substituted with a LATITUDE remote follow-up.

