## 10.2. Point of Study Exit

All subjects enrolled in the clinical study (including those withdrawn from the clinical study or lost to follow-up) shall be accounted for and documented. Study subjects can exit the study for the following reasons: study completion (subject completed 5 years of follow-up), death, or withdrawal. If a subject withdraws from the clinical investigation, the reason(s) shall be reported.

Reasons for withdrawal include, but are not limited to: adverse event, Investigator discretion, Lost to follow-up, RV lead no longer in service, transplant or removal of target organ, or subject withdrew from participation in study. While study withdrawal is discouraged, subjects may withdraw from the study at any time, with or without reason, and without prejudice to further treatment. All applicable case report forms up to the point of subject withdrawal and an "End of Study" form must be completed. Subjects who are "lost-to-follow-up" should have documented attempts to contact them prior to completion of the "End of Study" form.

Additional data may no longer be collected after the point at which a subject has been withdrawn from the study or withdraws his/her consent, for whatever reason. All open adverse events should be closed or documented as chronic. Data collected up to the point of study subject withdrawal may be used.

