#### **11.5.1. Missed Bi-Annual Study Subject Follow-Up Visits**

In the event that a Bi-Annual Study Subject Follow-Up Visit is missed, investigational site/center personnel are expected to make every effort to contact the study subject (*e.g.*, via certified mail, telephone calls, Email messages, etc.) in order to determine the subject's status. Study subjects are considered "lost-to-follow-up" after three (3) documented contact attempts and should be immediately withdrawn from the study if investigational site/center personnel have not had any contact with a study subject after three attempts. The date of the study subject's last in-clinic follow-up visit (scheduled or unscheduled) will be used as the date that he/she was "lost-to-follow-up" and therefore ended their participation in the study. Study subjects will be withdrawn at any time if they express their desire to cease their participation in the study.

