#### **12.1.2. Endpoint-related Adverse Events**

Inclusion of adverse events in the endpoint is based on the adjudication of the adverse event by the independent Clinical Events Committee (CEC), and on the time of occurrence of the adverse event.

The following adverse events will all be reported, and those adverse events that result in permanent loss of therapy, invasive intervention, injury or death will be included in the endpoint analysis regardless of cause or time of occurrence:

- Pneumothorax;
- Perforation; and
- Cardiac tamponade.

The following adverse events, occurring at 30 days or less from lead-related surgery, will all be reported, and those adverse events that result in permanent loss of therapy, invasive intervention, injury or death and that are also determined to be attributable to a structural lead/header failure by the Clinical Events Committee (CEC) will included in the endpoint analysis:

- Right ventricular lead dislodgment;

- Extra-cardiac (diaphragmatic/pectoral) stimulation caused by the RV lead;
- Inability to place or position the right ventricle (RV) lead;
- Implant procedure-related complications such as arrhythmias and hematoma formations;
- Infection;
- In-patient damage to RV lead (*e.g.*, accidental cut to lead body during pocket revision, device replacement, etc.);
- Other procedure-related adverse events identified at implantation;
- Lead under-insertion identified at implant; and
- Loose header set screws identified at implant.

The following adverse events, occurring more than 30 days after lead-related surgery, will all be reported, and those adverse events that result in permanent loss of therapy, invasive intervention, injury or death will be included in the endpoint analysis for the 4-SITE Lead/Header System:

- Right ventricular lead dislodgment;
- Extra-cardiac (diaphragmatic/pectoral) stimulation caused by the RV lead;
- Low/High impedance values; and
- High right ventricle (RV) pacing threshold with sudden change (>2 volts), intermittent RV capture and non-capture of the RV lead.

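### The subgroup test in 12.3.3 uses logistic regression on a censored five-year endpoint, so unequal follow-up between subgroups biases the comparison

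*Combined protocol and SAP*

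**What the plan says.** Section 12.3.1 defines the primary analysis as a Kaplan-Meier estimate of the five-year complication-free rate, starting at implant. On incomplete follow-up it states: "The censoring mechanism of the Kaplan-Meier analysis incorporates all available data on study subjects, including those that withdrew or were lost-to-follow-up". On the analysis set: "All subjects who are successfully implanted with the 4-SITE Lead/Header System will be included in the analysis".

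Section 12.3.3 then compares the primary endpoint between subgroups by sex, geography, age and enrollment timing: "The baseline covariate will be added to a univariate logistic regression model and a test for significance at the 5% level will be performed". Where a covariate is significant, "the results for each subgroup will be presented separately". The section names no time variable, offset, weighting or completer set, and gives no rule for subjects with less than five years of follow-up.

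Early exit is part of the design. Section 8 follows subjects for five years "or until death, withdrawal from the study, or termination/closure of the study". Section 10.2 lists: "Reasons for withdrawal include, but are not limited to: adverse event, Investigator discretion, Lost to follow-up, RV lead no longer in service", among others. Section 13.3.10 requires withdrawal once the RV lead is explanted or out of service. For subjects lost to follow-up, section 11.5.1 sets the exit date: the "last in-clinic follow-up visit (scheduled or unscheduled) will be used as the date".

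**The concern.** The two sections treat one endpoint in two ways. Kaplan-Meier credits each subject with the time actually observed. A yes/no logistic model cannot, so every subject who leaves early without a complication must be forced into a category:

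- **Counted as complication-free.** Risk is understated, and more so in the subgroup that leaves earlier.
- **Excluded.** Risk is overstated, again more so in the subgroup that leaves earlier.

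The inclusion sentence in 12.3.1 may rule out exclusion. It stands in the Kaplan-Meier paragraph, though, so carrying it over to 12.3.3 is an inference. Neither choice recovers the rate defined in 12.3.1.

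At stake is whether the test flags a subgroup difference that is not there, or hides or exaggerates one that is. In a surveillance study, that flag should not depend on who left earlier.

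**Working it through.** **Inputs from the documents.** At least 1,780 implanted subjects (8.1); five years of follow-up (8); a 5% test level (12.3.3). The plan gives no figure for the performance of this test, so there is none to reproduce. The sample-size parameters in 12.1.4 are blacked out.

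**Assumptions.** A 50:50 split (890 per group), a two-sided test, and exponential censoring independent of events, stated as the share censored by year 5 if no event occurred. Event timing is varied because 12.1.2 includes some implant-type complications (pneumothorax, perforation, tamponade) that "will be included in the endpoint analysis regardless of cause or time of occurrence" if they have the listed consequences. Early events are therefore possible.

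**Formulas.** For five-year risk r, share s of events at implant and censoring c:

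- p0 = s·r; l = −ln(1 − (r − p0)/(1 − p0))/5; m = −ln(1 − c)/5
- Counted as complication-free: P1 = p0 + (1 − p0)·l/(l + m)·(1 − exp(−5(l + m)))
- Excluded: P2 = P1/(P1 + (1 − p0)·exp(−5(l + m)))
- Rejection rate from the Wald test of the log odds ratio, with 890 per group (fewer after exclusion)

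**Worked case: r = 5% in both groups, s = 0.** l = −ln(0.95)/5 = 0.01026.

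- c = 40%: m = 0.10217, exp(−5(l + m)) = 0.95 × 0.60 = 0.57. P1 = (0.01026/0.11242) × 0.43 = 3.92%. P2 = 0.0392/(0.0392 + 0.57) = 6.44%.
- c = 20%: m = 0.04463, exp(−5(l + m)) = 0.95 × 0.80 = 0.76. P1 = (0.01026/0.05489) × 0.24 = 4.49%. P2 = 0.0449/(0.0449 + 0.76) = 5.57%.
- The true odds ratio is 1.00. The expected one is 0.87 (complication-free coding) or 1.17 (exclusion).
- For complication-free coding, ln(0.870) = −0.140 with standard error 0.237, a ratio of −0.59. The rejection rate is Φ(−1.37) + Φ(−2.55) = 9.1%. The same steps give 9.9% for exclusion.

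**False positives at equal true risk of 5%.** The log-rank column is simulated, 10,000 trials per scenario, with a Monte Carlo standard error of about 0.2 points.

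| Event timing | Censored | Complication-free coding | Exclusion | Log-rank |
|---|---|---|---|---|
| Constant hazard | 30% vs 30% | 5.0% | 5.0% | 4.8% |
| Constant hazard | 35% vs 25% | 6.0% | 6.2% | 5.2% |
| Constant hazard | 40% vs 20% | 9.1% | 9.9% | 4.8% |
| Quarter at implant | 40% vs 20% | 7.2% | 13.0% | 5.1% |
| Half at implant | 35% vs 25% | 5.2% | 7.8% | 4.8% |
| Half at implant | 40% vs 20% | 5.9% | 16.7% | 5.3% |

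**Baseline risk varied** (complication-free coding, constant hazard, 40% vs 20%): 6.6% at a risk of 2%, 7.4% at 3%, 8.2% at 4%, 9.1% at 5% and 11.3% at 7.5%.

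**Detection of a true 7.5% vs 5%.** Censoring in the higher-risk group is given first.

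| Event timing | Censored | Complication-free coding | Exclusion | Log-rank |
|---|---|---|---|---|
| Constant hazard | 30% vs 30% | 51% | 51% | 52% |
| Constant hazard | 35% vs 25% | 38% | 65% | 51% |
| Constant hazard | 25% vs 35% | 63% | 37% | 51% |
| Constant hazard | 40% vs 20% | 27% | 77% | 51% |
| Constant hazard | 20% vs 40% | 74% | 24% | 52% |
| Half at implant | 35% vs 25% | 48% | 74% | 56% |
| Half at implant | 25% vs 35% | 61% | 33% | 55% |
| Half at implant | 40% vs 20% | 42% | 88% | 55% |
| Half at implant | 20% vs 40% | 66% | 16% | 55% |

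In the same simulation the logistic results agreed with the closed form within 1.5 points.

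**The case against.** - **No documented trigger.** The bias needs censoring that differs between subgroups, and nothing in the documents shows that it does. All subjects share one visit schedule, and the primary analysis waits for the last subject's five years, although the partly redacted closure rule in 8.2 could end follow-up sooner. This stands: the point is conditional, and at 35% vs 25% the inflation is small.
- **Exclusion drives the largest figures.** Also fair. If 12.3.1 fixes complication-free coding, the worst false-positive rate at 5% risk is 9.1%. With half of events at implant it is near nominal (5.9%), and what remains is the effect on detection, 42% to 66% against about 55%.
- **Deaths.** Counting a death without complication as complication-free targets a cumulative incidence, which is a legitimate quantity. But it is not the Kaplan-Meier rate of 12.3.1, and 12.3.3 says that it tests the primary endpoint. The calculation does not separate deaths from withdrawals, so part of the effect is a change of estimand rather than an error.
- **Log-rank is favored by the simulation.** It holds its level because censoring was drawn independently of events. Withdrawal for an adverse event or for a lead out of service could break that assumption. The primary Kaplan-Meier analysis needs the same assumption, so the replacement adds no new one, but its advantage was not tested under dependent censoring.
- **Section 12.3.4 also uses logistic regression.** True. The center test was not quantified here and no change to it is claimed. That does not weaken the case for 12.3.3.

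**Conclusion.** The concern holds, as an improvement at little cost rather than a threat to the study's conclusion. Section 12.3.3 tests a censored endpoint with a model that has no place for follow-up time, and no visible text repairs this. With equal censoring the two methods agree and the replacement loses no power. With 40% vs 20% censored, constant hazard and complication-free coding, false positives run from 6.6% to 11.3% as baseline risk goes from 2% to 7.5%. Detection of a true difference moves up or down according to which group leaves earlier. These sizes rest on assumed censoring, event timing and risk; the direction of each bias does not depend on the exact values. The consequence is limited to which subgroup results are flagged and shown separately. No decision rule depends on the test.

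**What to change.** In 12.3.3, replace the univariate logistic regression with a univariate Cox model or log-rank test on time to first endpoint complication, using the time origin and censoring of 12.3.1. Where subgroups are presented separately, give the five-year Kaplan-Meier rate with confidence bounds for each, so that the flag and the display rest on the same quantity.

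The cost is one sentence, with no extra data or subjects. The time variable is already needed for the Kaplan-Meier plot in the six-monthly reports (12.3.6). Section 12.3.2 allows the change through an amended SAP approved before the analysis. If the sponsor treats it as a protocol revision affecting scientific integrity, section 14 requires approvals, and it can go with the next amendment.

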## **9. Subject Selection**

### **9.1. Study Population and Eligibility**

Investigators are expected to approach all potentially eligible study subjects who have been (within 14 calendar days post implant window), or will be, implanted with the 4-SITE Lead/Header System at the investigational center for enrollment into this study until the

enrollment ceiling is reached. All study subjects must meet all the inclusion criteria and none of the exclusion criteria (listed hereinafter in Sub-sections 9.2 and 9.3, respectively). Investigational centers are encouraged to enroll subjects in the LSS of 4-SITE Study prior to the implantation of the 4-SITE Lead/Header System. However, a maximum of fifty percent (50%) of the study subjects may be enrolled up to 14 calendar days post device system implant as long as the required data are available from/since the implant. The required data for a post-implant enrollment must include the following implant information and data:

- Right ventricle (RV) lead and pulse generator (PG) date of implant;
- RV lead and PG model and serial numbers;
- RV lead implant attempts/repositioning (whether more than one lead or lead position was attempted to achieve a successful lead implant);
- RV lead electrical measurements for final lead configuration (*i.e.*, sensing, pacing threshold and impedance values from the implanted PG device);
- Assessment and documentation of the absence/presence of adverse events by reviewing available patient medical records including, but not limited to, the following:
  - Progress notes;
  - Laboratory reports;
  - Operations reports; and
  - Discharge summary.

For study subjects enrolled after device system implant (within 14 calendar days), the required One-Month Post-Implant Follow-up Visit is still required. Study subjects will then continue to have a complete device system interrogation at least once every six (6) months from the date of their device system implant for a five (5) year term. A deviation must be reported if a study subject is not seen within the follow-up visit window (*i.e.*, 6 months +/- 30 days).

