## 10.4. Enrollment Controls

Investigational centers will be notified to cease enrolling patients for this study when the enrollment target is reached, or at the Sponsor's discretion in consultation with the FDA. This notification is expected to happen when at least 1,780 study subjects have been enrolled and successfully implanted with the 4-SITE Lead/Header System. In order to ensure geographical dispersion of investigational sites, individual study sites may not enroll more than twenty percent (20%) of the anticipated enrollment ceiling of 1,780 subjects (*i.e.*, not more than 356 subjects at any single site). For the study overall, no more than 50% of patients will be enrolled post-implant.

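### Enrollment timing and geography are compared only in separate univariate models, so a regional imbalance in timing could distort the pre- versus post-implant subgroup result

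*Combined protocol and SAP*

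**What the plan says.** Section 12.3.3 lists sex, geography (International or United States), age (below 65, or 65 and over) and enrollment timing (pre- or post-implant). The list is open: it "includes, but is not necessarily limited to, the following". The method is: "The baseline covariate will be added to a univariate logistic regression model and a test for significance at the 5% level will be performed". The only stated consequence is: "For each baseline covariate in which a significant difference exists between subgroups, the results for each subgroup will be presented separately".

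Two other sections govern how subjects come to be pre- or post-implant. Section 9.1 says: "Investigational centers are encouraged to enroll subjects in the LSS of 4-SITE Study prior to the implantation of the 4-SITE Lead/Header System". It also expects investigators to approach all eligible patients in either window. Section 10.4 sets the limit: "For the study overall, no more than 50% of patients will be enrolled post-implant". No limit by region or site is stated.

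Section 12.3.4 adds a random-effects logistic model for center, described only as a test of the center variance. No section gives a joint, stratified or adjusted comparison of timing and geography.

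**The concern.** Timing is an observed factor, not a randomized one. With up to 200 centers on several continents and only a study-wide limit, post-implant enrollment could be concentrated in some regions. If complication risk also differs by region, for whatever reason, a timing-only model attributes part of the regional difference to timing. If timing truly matters, the geography-only model has the mirror-image problem.

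Timing deserves a clean comparison because the two groups are observed differently in the first days. The Kaplan-Meier clock starts at implant (Section 12.3.1). Pneumothorax, perforation and tamponade with a qualifying outcome count whenever they occur (Section 12.1.2). Post-implant subjects may consent up to 14 days later, need complete implant data (Section 9.3), and have an optional pre-discharge interrogation (Section 8). Selection or under-ascertainment could therefore make them look better. The timing comparison in Section 12.3.3 is the only listed analysis that could show this. A false signal would present timing as if it mattered; a masked one would reassure wrongly.

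**Working it through.** The plan gives no power or error figure for the subgroup tests, so there is nothing of its own to reproduce here. The check asks how far the univariate timing test can move under stated assumptions.

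**Inputs from the documents**
- 1,780 subjects (Section 8.1).
- At most 125 of 200 centers in the US (Section 8.1): 125/200 = 62.5%, used as the US share of subjects. This is an assumption, because these are maximum center counts.
- Post-implant share at most 50% overall (Section 10.4).
- Test at 5% (Section 12.3.3); two-sided is assumed, since the side is not stated.

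**Assumed inputs**
- Post-implant share by region and five-year complication risk by region. The documents give neither.
- Five-year status known for everyone.

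**Step 1: worked case with no true timing effect.** Post-implant share 32% US and 80% International; risk 4% US and 7% International.
- Overall post-implant share: 0.625×0.32 + 0.375×0.80 = 0.20 + 0.30 = 0.50, which is 890 per group.
- Post-implant risk: (0.20×0.04 + 0.30×0.07)/0.50 = 5.80%.
- Pre-implant risk: (0.625×0.68×0.04 + 0.375×0.20×0.07)/0.50 = 4.45%. The risk ratio is 5.80/4.45 = 1.30.
- Standard error: √[(0.058×0.942 + 0.0445×0.9555)/890] = 0.01045. Mean z = 0.0135/0.01045 = 1.29.
- P(significant) = Φ(1.29 − 1.96) + Φ(−1.29 − 1.96) ≈ 0.25.

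**Step 2: milder mix.** With 40% and 67% post-implant and the same risks, the group risks are about 5.5% and 4.75%. The mean z is 0.0075/0.01045 = 0.72, and P(significant) ≈ 0.11.

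**Step 3: simulation over a range.** 1,780 subjects, 62.5% US, 1,000 replicates per row, no true timing effect. The timing-only logistic model is compared with timing plus geography.

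| Post-implant share, US/Intl | Risk, US/Intl | Timing only: rejects (median OR) | With geography: rejects (median OR) |
|---|---|---|---|
| 40/40 | 4%/8% | 6% (1.01) | 6% (1.01) |
| 20/80 | 5%/5% | 5% (1.00) | 5% (1.00) |
| 30/50 | 4%/8% | 12% (1.17) | 4% (1.00) |
| 20/80 | 4%/6% | 20% (1.30) | 5% (1.01) |
| 30/70 | 4%/8% | 27% (1.33) | 5% (1.01) |
| 20/80 | 4%/8% | 57% (1.56) | 5% (1.01) |

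Monte Carlo error at a true 5% is √(0.05×0.95/1,000) = 0.7 percentage points. The first two rows show that the problem needs both conditions: with an equal mix or equal risk, the univariate test behaves correctly.

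**Step 4: masking.** Assume a true timing odds ratio of 2, baseline risk 8% US and 4% International, and post-implant share 20% US and 80% International. The timing-only model gives a median odds ratio of 1.33 and rejects in 39% of trials. With geography it gives 2.00 and rejects in 93%. With an equal 43% mix in both regions, the timing-only model rejects in 98%, so the loss comes from the imbalance.

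**The case against.** The strongest reply is that Section 12.3.3 asks a descriptive question, whether endpoint results differ between subgroups, and an unadjusted comparison answers it. The plan makes no causal claim about timing. That stands as far as it goes, but a reader shown pre- and post-implant results separately will want to know whether timing or region explains the gap, and the plan gives no means of telling.

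Second, a reader might infer that this test decides whether pre- and post-implant subjects may be pooled. The documents do not support that. Section 12.3.1 includes every successfully implanted subject whatever the subgroup tests show, and the only analysis labelled pooling is by center (Section 12.3.4).

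Third, a reader might take it as given that sites choose the timing. That too is inference: the text encourages pre-implant enrollment and expects all eligible patients to be approached. What stands is that nothing in the plan balances timing across regions.

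Fourth, the size rests on assumptions, and the 25% case places post-implant enrollment at the full 50% limit. This stands, and the result must be stated as conditional.

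Fifth, the planned geography test would often expose the regional difference. In the Step 1 case, with about 1,112 US and 668 International subjects, the standard error is √(0.04×0.96/1,112 + 0.07×0.93/668) = 0.0115, z = 0.03/0.0115 = 2.61, and power is about 74%. That softens the harm but does not show how much of the timing difference region explains.

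**Conclusion.** The point holds as a minor one. The timing and geography comparisons are unadjusted, timing is not assigned, and the timing result can be distorted in either direction if both the timing mix and the risk vary by region. Under the assumed inputs, the false-positive rate runs from 5% with an equal mix or equal risk, through about 11% and 25% in the worked cases, to 57% in the most extreme case simulated. Adding geography returns it to 4–6% in every simulated row. These figures assume 62.5% US subjects and complete five-year status. Whether the actual study sits near 5% or well above it cannot be judged from the documents.

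It would be wrong to infer that the main result is at risk. The pooled Kaplan-Meier estimate and its comparison with 92.5% (Section 12.1.3) do not depend on these tests, and the plan contains no pre/post poolability rule that could go wrong. What is affected is the subgroup interpretation and which results are presented separately.

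**What to change.** In Section 12.3.3, keep the univariate screen and its rule for separate presentation, and add:
- one prespecified supportive multivariable model for the primary endpoint with sex, geography, age and enrollment timing together;
- adjusted timing and geography effects with 95% intervals;
- a table of enrollment timing by region;
- a sentence saying that the timing subgroup result is interpreted from the adjusted effect, and that this analysis is descriptive and does not alter the primary analysis.

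The cost is one model and one table. Age and gender are collected at enrollment (Sections 11.1.1 and 11.1.2), timing and geography are known for every subject, and Section 12.3.2 already provides for an amended SAP before analysis. In the Step 1 case there would be about 1,780 × (0.625×0.04 + 0.375×0.07) = 91 events with complete follow-up, or about 23 per model term; censoring would lower this.

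There are two downsides. Intervals widen slightly when covariates are correlated. Because geography is only binary, differences between centers and among the international regions remain unadjusted, and the text should say so.
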